5.3. Exploratory Outcomes

Efficacy of vadadustat to induce known transcriptional targets of HIFs (e.g., erythropoietin, extracellular adenosine levels, circulating levels of CD73, VEGF, hypoxia-driven microRNAs that dampen lung inflammation) will be explored.

[figure not shown]
Various laboratory measurements (e.g., serum creatinine, FGF-23, markers of attenuated inflammation) will be measured and summarized.

6. Study Population

6.1. Eligibility Criteria

6.1.1. Inclusion Criteria

- 1. Men and women ≥ 18 years of age
- 2. Laboratory-confirmed diagnosis of COVID-19 by detection of SARS-CoV-2 RNA by RTPCR from any specimen respiratory
- 3. Admitted to the hospital within 36 hours
- 4. For patients admitted WITH respiratory symptoms, enrollment must occur within 36 hours of hospital admission. If the patient is admitted to the hospital with normal saturations, but develops respiratory symptoms DURING their hospital stay, enrollment may occur within 24

hours of desaturation to 94% or less on room air.

- 5. Oxygen saturation of hemoglobin by pulse oximetry at room air $\leq 94\%$
- 6. Understands the procedures and requirements of the study and provides written informed consent and authorization for protected health information disclosure

6.1.2. Exclusion Criteria

- 1. Hypersensitivity to vadadustat or any of its excipients
- 2. Placed on mechanical ventilation before randomization
- 3. Hemoglobin above the gender-specific upper limit of normal (ULN) at randomization: 16 g/dL for females and 18 g/dL for males
- 4. Patients who have erythrocytosis or polycythemia vera
- 5. Patient taking Probenecid, lopinavir or ritonavir.
- 6. Women who are pregnant or breastfeeding, or positive pregnancy test before randomization
- 7. Patients not on maintenance dialysis with eGFR<31ml/min.
- 8. Patients who have received a solid organ transplant, heart, kidney, liver or lung
- 9. Patients who are prisoners
- 10. Patients who are currently Do Not Resuscitate (DNR) or Do Not Intubate (DNI)
- 11. Patients with modified Rankin scale of 3 or greater
- 12. Patient who are currently enrolled in any other interventional clinical trial
- 13. Acute thromboembolism
- 14. Home oxygen (O2)

7. Study Drug

7.1. Dosage

Vadadustat 900 mg or matching placebo

7.2. Route and Form

Oral 150 mg tablets and matching placebo

7.3. Administration to Intubated Patients

Tablets can be crushed using a pill crusher and administered to an intubated patient through a nasogastric tube. Tablets may be dissolved in warm water after cutting the pill in half.

The research pharmacist or designee will dispense study drug to the patient and maintaining study drug accountability as described below.

7.4. Vadadustat

Refer to the Vadadustat Pharmacy Manual for details on the shipping, dispensing, storage, destruction, and accountability of vadadustat tablets.

7.4.1. Storage and Supplies

Vadadustat will be provided as 150 mg, white to off-white, round, biconvex film-coated, debossed or non-debossed tablets for oral administration. The tablets and matching placebo will be packaged in high density polyethylene bottles with child resistant closures, polypropylene liner, and induction seal.

Vadadustat and placebo will be stored per the investigational study drug label in a temperature controlled, locked facility, accessible only to authorized study personnel.

7.4.2. Dispensing of Vadadustat or Placebo

Patients will receive one of the following doses for 14 days, or until their date of discharge, or whichever comes first, vadadustat 900 mg (6 tablets once daily) or matching placebo (6 tablets once daily) without regard for meals at approximately the same time each day.

7.4.3. Vadadustat Accountability and Destruction

All vadadustat will be accounted for and all discrepancies explained. The research pharmacy is responsible for keeping accurate records of the clinical supplies received from Akebia Therapeutics (Akebia) all supplies retained in inventory at the study site, and study drug dispensed to or returned from each patient. Records will be maintained that accurately reflect the drug accountability of vadadustat.

Drug accountability includes, but is not limited to:

- Monitoring expiration dates.
- Verifying physical inventory matches documented inventory.

Verifying accountability records are completed for all vadadustat received, dispensed, and returned, and that all required fields are complete, accurate, and legible. During the study, the research pharmacist will be notified of any expiration dates or retest date extensions of study drug. If an expiration date notification is received during the study, the study site will complete all instructions outlined in the notification, including segregation of expired study drug for return to the Akebia or its designee for destruction as specified by the Akebia.

Prior to study site closure and at appropriate intervals during the study, the research pharmacist of designee will perform study drug accountability and reconciliation.

At the end of the study, the investigator will retain all original documentation regarding study drug accountability, return, and/or destruction, and copies will be sent to the sponsor.

All unused and/or partially used vadadustat will be returned to Akebia or destroyed at the study site, as specified by Akebia. Appropriate records of the disposal will be documented and maintained. No unused vadadustat may be disposed of until fully accounted for by Akebia or designee. Empty containers may be disposed of according to local procedures with the permission of Akebia.

7.4.4. Dosing rationale

The planned dosing is a fixed daily dose of 900 mg (supplied as 6-150 mg tablets). We believe that the dose and magnitude of HIF stabilization needed to induce the hypothesized beneficial pulmonary effects are the same as that needed to induce erythropoiesis. In healthy volunteers who received single doses of vadadustat, the median tmax ranged between 3.5 hours for the subjects who were administered 900 mg. The peak erythropoietin concentration was reached after 18 hours from dosing. In healthy volunteers who received 10 daily doses of vadadustat, the mean change in hemoglobin from baseline to day 11 among those who took vadadustat 900 mg was 0.43 g/dL. From published literature on COVID-19 patients, the median duration from onset of illness to admission is 7 days and takes a median of additional 3.5 days until ICU admission. In order to maximize the benefit of acute HIF stabilization and observe a potential benefit, a dose of 900 mg once daily for 14 days is recommended.

Vadadustat doses of 150-1200 mg per day were tested in healthy volunteers and patients with anemia secondary to chronic kidney disease (CKD). A dose of vadadustat 900 mg was administered to healthy volunteers and patients with CKD for 10 days without significant adverse effects. In healthy volunteers, the most commonly reported AEs (nausea, diarrhea, abdominal pain, flatulence, dyspepsia, headache, and dizziness) were generally reported to be mild to moderate in severity. There were no SAEs, deaths, or withdrawals due to AEs, and no clinically relevant changes in mean laboratory values, vital signs or ECGs. In CKD subjects, the most commonly reported AEs were nausea, diarrhea, vomiting, hypertension, hypotension, coronary artery disease, chronic and acute renal failure, gastroenteritis, urinary tract infection, and pneumonia.

8. Study Procedures

8.1. Recruitment

All COVID-19 patients will be screened for eligibility. If a patient meets screening eligibility, the study coordinator will introduce the study to the patient to determine interest. If the patient is interested in participating in the study, the study coordinator will introduce the patient to one of the study clinicians either in person or virtually utilizing WebEx. Written consent will be obtained for all patients interested in study participation. Patients will be randomized if meeting all eligibility criteria (as specified in inclusion/exclusion criteria). Initial recruitment will occur at MHH-Southwest and MHH-Texas Medical Center for the first 30 patients. After 30 and then 120 patients are treated, screening and enrollment will be suspended (suspension of enrollment will occur at n = 30, based on DSMB recommendation, enrollment will continue during the safety analysis at n = 120) to enable an interim blinded safety analyses by the DSMB. The DSMB will provide a report to the UTHealth COVID-19 Research Workgroup and UTHealth IRB to consider further patient screening and enrollment.

8.2. Concomitant medication

Probenecid is not allowed as it may increase systemic exposure to vadadustat. Investigators should adjust the dose of these concomitant medication as follows:

1. Simvastatin, maximum daily dose of 20 mg

2. Rosuvastatin, maximum daily dose of 10 mg

If the patient is currently taking erythropoiesis-stimulating agents or ESA (e.g., epoetin alfa, darbepoietin alpha, or methoxy polyethylene glycol-epoetin beta), the medication should be discontinued.

Sulfasalazine and other breast cancer resistance protein (BCRP) substrates (imatinib, gefitinib, nilotinib, prazosin, glyburide, cimetidine, AZT and lamivudine) should be used with caution as vadadustat can increase systemic exposure to these medications. Lopinavir and rotinavir are also prohibited due to observed higher LFTs in patients treated with these drugs.

Phosphate binders (iron-containing and non-iron containing) and oral iron supplements should be taken at least 2 hours before or after the dose of vadadustat as they can interfere with vadadustat absorption.

At enrollment, the study team will notify the treating physician of medications prohibited by the study. Study personnel will review the patient's current medications daily to identify the use of any prohibited medications and notify the treating physician when they are prescribed. The study team will discuss the use of alternative medications. If the prohibited medication cannot be stopped the patient will continue in the study but study medication will be stopped.

8.3. Complete Withdrawal from Study Visits/Assessments

A patient has the right to withdraw consent for participation in the study at any time. Withdrawal of consent is a patient's refusal to continue study treatment, data collection and ALL methods of follow-up noted in the informed consent form: procedures, participation in reduced procedures/study visits, telephone contact only or alternative contact only, source document or designated alternative contact, or access to medical records from alternative sources.

[figure not shown]
It is important for the Investigator to review options with a patient. The patient may decide to stop study medication but still be followed up in the hospital and contacted on Day 7, 14, and 28 after discharge to assess safety and efficacy outcomes. Alternatively, the patient may decide to completely withdraw consent from the study which entails not receiving study medication, not to be followed up in the hospital, and not to be contacted after discharge.

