5.1. Assessment of Efficacy

5.1.1. Primary Outcome

The proportion of patients at day 14 who are dead (8) or hospitalized, on invasive mechanical ventilation or ECMO (7) or hospitalized, on non-invasive ventilation or high flow oxygen devices (6) on the NIAID-OS.

[figure not shown]

Table 4: National Institute of Allergy and Infectious Disease Ordinal Scale (NIAID-OS)

Death	8
Hospitalized, on invasive mechanical ventilation or extracorporeal membrane oxygenation (ECMO)	7
Hospitalized, on non-invasive ventilation or high flow oxygen devices	6
Hospitalized, requiring supplemental oxygen	5
Hospitalized, not requiring supplemental oxygen – requiring ongoing care (COVID19 related or otherwise)	4
Hospitalized, not requiring supplemental oxygen – no longer requires ongoing medical care	3
Not hospitalized, limitation on activities and/or requiring home oxygen	2
Not hospitalized, no limitations on activities	1
Source: https://clinicaltrials.gov/ct2/show/NCT04421027?cond=COVID19&lead=Lilly&draw=2&rank=1	•

5.1.2. Secondary Outcomes:

Proportion of patients with a score of 0 at 14 days on the MSOFA scale.

Organ System	0	1	2	3	4
Respiratory SpO2/FiO2	> 400	≤ 400	≤ 315	≤ 235	≤ 150
Liver	No scleral icterus or jaundice			Scleral icterus or jaundice	
Cardiovascular, hypotension	No hypotension	MAP < 70 mm Hg	Dopamine ≤ 5 or dobutamine any dose	Dopamine > 5 Epinephrine ≤ 0.1 Norepinephrine ≤ 0.1	Dopamine > 15 Epinephrine > 0.1 Norepinephrine > 0.1
CNS, Glasgow Coma Score	15	13 – 14	10 - 12	6 – 9	< 6
Renal, Creatinine mg/dL	< 1.2	1.2 – 1.9	2.0 - 3.4	3.5 - 4.9	> 5.0

Table 3: Modified Sequential Organ Failure Assessment (MSOFA) Score

Source: Grissom et al, 2010

Note: Discharged patients will be assigned a 0 score and dead patients a score of 20.

5.1.3 Other Outcomes:

• Average mSOFA scores at day 7 and day 14, gathered either from in-hospital labs and clinical notes for inpatients, or from calling discharged patients

- Ventilator-free survival at day 7 and day 14, as assessed by the patient's best score on the NIAID-OS on day 7, day 14 and day 28
- Overall survival at day 7, day 14 and day 28
- Proportion of patients with hypotension (MAP <70 mm Hg or requirement for inotropes or vasopressors to maintain blood pressure) at day 7 and day 14
- Proportion of patients with acute kidney injury at day 7 and day 14
- Time to hospital discharge

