8.4. Data Collection

Refer to *Appendix 1 (Schedule of Activities)* for detailed timing and frequency of the below activities:

- Informed consent
- Demographic and contact information
- Oxygen saturation by pulse oximetry
- Pregnancy test (collected only at baseline)

٠

- Hemoglobin, creatinine, liver function test (AST, ALT, Bilirubin) at baseline, day 7, day 14 and during long term follow up visits at 6mo, 12mo and 24mo (If the patient remains hospitalized after 14 days, or the drug is discontinued for any reason, creatinine and hemoglobin lab values will be collected for up to 2 days following the last dose, again ceasing upon discharge.)
- Height, weight, BMI
- Eligibility, at baseline
- Randomization
- Blood biomarkers (during hospitalization only) \circ Baseline, Day 7 and Day 14 (10 cc each collection)
- Urine biomarkers (during hospitalization only)
 o Baseline, Day 7 and Day 14 (5 cc each collection)
- Medical/Medication history
- Study medication dosing
- AE and SAEs
- Concomitant medications and COVID-19 specific treatment other than vitamins and minerals
- Modified SOFA, daily until discharge, & at Day 7, 14, and 28, with discharged patients receiving a score of 0 and deceased patients receiving a score of 20.
- NIAID-OS, daily and until discharge and at Day 7, 14, and 28
- For patients who are discharged, before or after completing 14 days of in-hospital treatment, a phone visit at day 7, 14, and 28 after randomization will be conducted to collect serious adverse events and NIAID-OS score.

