11.8 Follow-up of Unresolved Events

All AEs will be followed until they are resolved, or the investigator assesses them as chronic or stable or the subject's participation in the study ends (i.e., until a final report is completed for that

subject).

All SAEs and non-serious events that are ongoing at the time a subject's participation in the study ends and that are assessed by the investigator as related to the study drug, will continue to be followed until they resolve or until the investigator assesses them as "chronic" or "stable". Followup information will be reported to UTHealth on the appropriate CRF or paper SAE Report Form if EDC is unavailable.

More details of the study safety plan are described in the study Manual of Procedures.

12. Sample Size and Power Calculation

The trial will investigate the superiority of vadadustat 900 mg per day to placebo for the prevention and treatment of ARDS among COVID-19 patients, defined by the proportion of patients at day 14 who are dead (8) or hospitalized, on invasive mechanical ventilation or ECMO (7) or hospitalized, on noninvasive ventilation or high flow oxygen devices (6) on the NIAID-OS (i.e. decrease in the proportion of participants with NIAID-OS ≤ 6 at day 14).

Anticipated sample size for the current study is N = 650. An evaluation by the DSMB will occur following ascertainment of 14-day safety outcomes for the first 30 patients that are randomized and dosed, and a second at the first 120 (i.e. n = 60 receiving Vadadustat).

[figure not shown]
Bayesian analysis for superiority will occur following ascertainment of outcome at fourteen days after randomization of N = 650 patients. We stipulate that a posterior probability of a > 2.5% decrease in the proportion of NIAID-OS \geq 6 as a function of treatment that is > 0.85 constitutes sufficient evidence to declare that the active treatment condition is superior to placebo. The prior distribution for analysis will be ~Beta(a= 1, b = 1), or in the presence of covarying for stratification factors ~Normal (µ=0, σ 2=1 x 10) for the coefficients in the log-form of the appropriate generalized linear model.

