13.1. Specific Statistical Hypothesis Primary Outcome

Among adult hospital admissions with lab-confirmed diagnosis of COVID-19, vadadustat 900 mg will demonstrate superiority to placebo as defined by a lower probability, at treatment day 14, of

death (8) or hospitalization, on invasive mechanical ventilation or ECMO (7) or hospitalization, on non-invasive ventilation or high flow oxygen devices (6) on the NIAID-OS. Generalized linear modeling will evaluate the probability of patients demonstrating this status at day fourteen of treatment as a function of treatment condition after covarying for stratification variables.

Secondary Outcome

Among adult hospital admissions with lab-confirmed diagnosis of COVID-19, vadadustat 900 mg will demonstrate superiority to placebo as defined by a higher probability, at treatment day 14, of recovery on the MSOFA scale (MSOFA = 0). Generalized linear modeling will evaluate the probability of patients demonstrating an MSOFA = 0 at day fourteen of treatment as a function of treatment condition after covarying for stratification variables.

[figure not shown]

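### Read literally, section 8.3 times the day-14 efficacy contact from discharge for patients who stop study drug, while sections 8.4 and 12 time it from randomization: a minor wording conflict to remove

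*Combined protocol and SAP*

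**What the plan says.** Section 5.1.1 defines the primary outcome as "The proportion of patients at day 14 who are dead (8") or at NIAID-OS level 7 or 6. It gives no origin for day 14, so the clock has to come from elsewhere.

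- **Section 8.4** covers discharged patients as a whole: "For patients who are discharged, before or after completing 14 days of in-hospital treatment", there is "a phone visit at day 7, 14, and 28 after randomization will be conducted to collect serious adverse events and NIAID-OS score".
- **Section 12** places the superiority analysis "following ascertainment of outcome at fourteen days after randomization of N = 650 patients".
- **Section 8.3**, on patients who stop study medication but remain in follow-up, has them "contacted on Day 7, 14, and 28 after discharge to assess safety and efficacy outcomes".
- **Section 13.1** models "the probability of patients demonstrating this status at day fourteen of treatment", and uses similar treatment-day wording in the hypotheses for the primary and secondary outcomes.
- **Section 11.4.1** lists SAE contacts for discharged patients on days 7, 14 and 28 without naming an origin.

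Section 8.4 refers to Appendix 1 (Schedule of Activities) for detailed timing. That appendix is not in the text available to me.

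**The concern.** Sections 8.3 and 8.4 both apply to a patient who stops study drug and then goes home. On a literal reading they give two different call dates, and nothing in the available text says which governs.

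This matters because NIAID-OS is scored daily only until discharge. After that, the phone contact is the scheduled source of the primary-outcome status. If the call is late and events are not dated, errors can go either way:

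- A death, or a readmission at level 6 or 7, between day 14 and the call could be counted as a day-14 event.
- A patient back in hospital at level 6 on day 14 but home again by the call could be missed.

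The patients on the later clock would be exactly those who stopped drug. The assessment date would then depend on something that happens after randomization and that treatment could influence. Section 7.4.4 lists nausea, diarrhea and vomiting among the common events in CKD subjects. The intention-to-treat analysis in 13.2 needs the same assessment day whether or not drug was continued.

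**Working it through.** **1. Clocks side by side**

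| Section | Who or what | Origin stated |
|---|---|---|
| 5.1.1 | Primary outcome, day 14 | none |
| 8.3 | Stopped drug, still followed; days 7, 14, 28 | discharge, if read literally |
| 8.4 | All discharged patients; days 7, 14, 28 | randomization |
| 10 | Completion of, or discharge before, 14 treatment days | randomization |
| 11.4.1 | AE window: 16 days, explained as 14 dosing days plus two | randomization |
| 12 | Primary analysis, day 14 | randomization |
| 13.1 | Hypotheses and models, treatment day 14 | not defined |

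The only clear conflict is 8.3 against 8.4 and 12. Section 13.1 is imprecise, but sections 10, 11.4.1 and 12 show that treatment days are counted from randomization.

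**2. Calendar effect of 8.3 read literally**

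For discharge on study day d, the contacts fall on days d + 7, d + 14 and d + 28. The values of d are illustrative.

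| d | 'Day 7' | 'Day 14' | 'Day 28' |
|---|---|---|---|
| 3 | 10 | 17 | 31 |
| 5 | 12 | 19 | 33 |
| 7 | 14 | 21 | 35 |
| 10 | 17 | 24 | 38 |
| 13 | 20 | 27 | 41 |

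The day-14 status would be read d days late, here 3 to 13 days. A patient still in hospital on day 14 has a daily score, so the primary outcome is exposed only when d is below 14.

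**3. The plan's own figure**

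Inputs: N = 650 at 1:1 (325 per arm), placebo rate 25.1%, Beta(1,1) priors, success if the posterior probability of a decrease above 2.5 points exceeds 0.85. With 4,000 simulated trials and a 15-point absolute decrease (25.1% to 10.1%), power is 99.9% against 99.1% stated, and type I error is 3.55% against 3.5% stated. These agree closely enough to use the rule as a yardstick. The stated powers at 12.5 and 10 points (96.1%, 86.3%) come out higher under the same rule (98.8%, 90.7%); that is a separate matter. None of these figures depends on the clock.

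**4. Size, under assumptions**

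The documents give no rate of stopping drug and no discharge times. Assume that a fraction f = 5–20% of an arm stops drug and is discharged before day 14, and that a net fraction q = 2–10% of those changes status between day 14 and day d + 14. The shift in that arm's event rate is s = f × q:

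- low: 0.05 × 0.02 = 0.1 point (0.3 of 325 patients)
- high: 0.20 × 0.10 = 2.0 points (6.5 of 325 patients)

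Now put the whole shift in the vadadustat arm and use the normal approximation, with z(0.85) = 1.036:

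- Type I error, shift in favour of vadadustat: Φ((s − 0.025)/SE − 1.036), SE² = [0.251 × 0.749 + (0.251 − s)(0.749 + s)]/325
- Power at a 10-point effect, shift against vadadustat: Φ((0.10 − s − 0.025)/SE − 1.036), SE² = [0.251 × 0.749 + (0.151 + s)(0.849 − s)]/325

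| s (points) | Type I error | Power at 10 points |
|---|---|---|
| 0 | 3.8% | 91.4% |
| 0.1 | 4.1% | 90.9% |
| 0.5 | 5.2% | 88.4% |
| 1.0 | 6.9% | 84.7% |
| 2.0 | 11.8% | 75.5% |

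The last row needs f and q both at the top of their ranges and the whole shift in one arm. A shift equal in both arms leaves type I error essentially unchanged.

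**The case against.** The best defence is that 'after discharge' in 8.3 names a setting and not a time origin. The sentence sets in-hospital follow-up against contact after discharge. The sentence that follows, on complete withdrawal, repeats the pair in a way that cannot be a time origin. Days 7, 14 and 28 are the protocol's standard visit labels. Section 8.3 is about withdrawal options; timing belongs to 8.4, which already covers every discharged patient from randomization. Appendix 1 may state the origin outright.

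The bias argument also has limits. A discharged patient is already below level 6 and becomes an event only through death or readmission at level 6 or 7. Section 7.4.4 gives no adherence data, and it reports no withdrawals due to AEs in healthy volunteers. A call after day 28 can still collect SAEs that occurred by day 28, so the window in 11.4.1 is not contradicted.

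Most of this stands, and it is why the point is minor. It does not remove the conflict. The 8.3 sentence attaches the day numbers directly to discharge and says that the contacts assess efficacy, so a coordinator could schedule from it in good faith. The available text has no rule of precedence.

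**Conclusion.** Section 8.3 is wrong as written and should be corrected, as a minor point. Followed literally, it would make the day-14 status of early-discharged drug-stoppers late by as many days as they had spent in the trial before discharge. The effect on the primary result is probably small; the 0.1 to 2.0 point range rests entirely on the assumed f and q. Nothing in the documents shows that any call was made on the discharge clock.

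Three stronger readings are tempting but not supported:

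- **A separate clock from first dose.** A reader might infer this from 13.1. That section does not mention first dose, and sections 10, 11.4.1 and 12 tie treatment days and the primary analysis to randomization.
- **No defined outcome for early discharges.** Drug is given "for 14 days, or until their date of discharge, or whichever comes first", so a reader might conclude that a patient sent home early never reaches the outcome day. But 8.4 requires a NIAID-OS from these patients at day 14 after randomization, the scale has levels 1 and 2 for patients not in hospital, and the note to the MSOFA table gives discharged patients a score of 0.
- **Most of the 650 affected.** The 25.1% planning figure is an event rate and says nothing about discharge timing.

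**What to change.** 1. In 8.3, end the contact phrase with 'after randomization, by phone if discharged' in place of 'after discharge'.
2. In 13.1, replace the treatment-day wording with 'day 14 after randomization', for both the primary and the secondary outcome.
3. State once, in 5.1.1, that all day numbers are counted from randomization whether or not study drug is continued. Check that 11.4.1 and Appendix 1 agree.
4. If any call was made on the discharge clock, set the day-14 NIAID-OS from the chart or from dated recall at the first contact on or after study day 14, and record that this was done.

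The cost is a few words in the protocol and a note to sites. No visits or calls are added, and sample size, priors and the decision rule stay as they are.
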